6. ECGs will be in triplicate (3 consecutive ECGs approximately 2 minutes apart). All ECGs will be sent to an ECG core laboratory vendor. ECG at screening will be used to determine patient eligibility. Ideally, the patient will be supine or reclined in a semi recumbent position for the entire infusion and for both pre- and post- infusion ECGs. To minimize artifact, the patient should not change position between the pre- and post-infusion ECGs. Additional ECGs may be done if clinically required. See [Table 2](#) for additional collection time points.
7. Pharmacokinetic samples: See [Table 2](#) for additional time points.
8. Medical History: To be collected within 28 days prior to first dose. Includes date of initial diagnosis with FAB subtype, prior AML therapies including HSCT and outcomes, and cytogenetics. Also, review study eligibility.
9. ECOG PS: Assessment is not required on Day 1 if acceptable screening assessment is done within 7 days prior to the start of investigational drug.
10. Patients with suspected extramedullary disease will have imaging assessment (eg, CAT or MRI) of all known disease sites.
11. Days 1, 4, and 7 laboratory samples should be collected prior to dosing.
12. Three times a week after GO dosing until determination of remission status (see [Section 7.5](#)); subsequently CBC and differential counts will be collected once weekly until EOT (or until start of Cycle 2 (if administered) or start of subsequent anticancer therapy).
13. Pregnancy test: Required in less than 7 days prior to Day 1.
14. Evaluations of HIV and hepatitis B serological tests and hepatitis C tests (see [Section 6.1](#)).
15. Efficacy evaluation and determination of remission status by blood and bone marrow aspiration (and biopsy if applicable) after recovery of blood counts is observed and/or at a maximum of 36 days after the last dose of GO treatment.
16. Adverse Event (AE) Assessments: Adverse events should be documented and recorded at each visit using NCI CTCAE version 4.03 up to 36 days after the last dose of GO or start of subsequent anticancer therapy, (eg, consolidation or conditioning regimen), whichever occurs first. Patients must be followed for AEs according to [Section 8](#). Sites should report related SAEs including VOD/SOS as warranted. Any occurrence of VOD/SOS is to be reported as SAE to Pfizer Safety and recorded in the case report form (CRF see [Section 7.4.1](#)).

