ADA = anti-drug antibody; D = Day; ECG = electrocardiogram; EOT = end of treatment; GO = gemtuzumab ozogamicin; NA = not applicable; NAb = neutralizing antibody; PD = pharmacodynamics; PK = pharmacokinetics

- PK samples collected during infusion should be taken from the arm OPPOSITE to the IV infusion site.
 PK sample should ALWAYS be collected AFTER ECG.
 If the dosing day is delayed, the PK and PD samples must be collected on the same day as dosing.
 PK collections on Day 4 and Day 10 for all patients.
- Pre-dose samples to be collected right before the start of GO infusion.
- 2-hour, post-dose samples are to be drawn right before the infusion ends (maximum window of ±10 minutes allowed).
- These post-dose samples to be drawn within ±10 minutes of the designated time.
- Samples on Days 10, 15, 21, and EOT visit may be collected at any time during the visit.
- Triplicate 12-lead ECG: At each time-point, three consecutive 12-lead ECGs will be performed approximately 2 minutes apart, but within 15 minutes for all ECGs, to determine the mean QTc. ECGs will be collected at Screening and on dosing Days 1, 4, and 7. It is preferable that the machine used has the capacity to calculate the standard intervals automatically. ECG interval readings by the ECG recorder's algorithm will be read and interpreted at the investigational site for eligibility determination. Additional ECGs will be performed as clinically indicated for patient safety monitoring and documentation stored in the source documents. ECG measurements will include PR interval, QT interval, RR interval and QRS complex.

C
 C
 T
 [REDACTED]

j. 24-hour, post dose samples for PK CCI [REDACTED] to be drawn from 24 to 30 hours of the designated time.

C l. EOT is defined as 36 days after the last dose of GO.

m. The follow-up for patients who are ADA positive at the EOT visit (36 days after last dose) consists of visits approximately every 90 days until ADA titers are no longer detectable, return to baseline, stabilize at a level acceptable to the investigator and sponsor, or up to 1 year after their first visit in the main study, whichever comes first.

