3. STUDY DESIGN

This is a single-arm, open-label, Phase 4 study evaluating the effect of GO on the QT, pharmacokinetics, safety, and immunogenicity of GO as a single-agent monotherapy in adult and pediatric patients with relapsed or refractory CD33-positive AML. Approximately 50 adult patients (age \geq 18 years) and 6 pediatric (12 years \leq age \leq 17 years) patients who satisfy the study eligibility criteria will be enrolled and treated with the fractionated regimen of GO 3 mg/m² on Days 1, 4, and 7 (up to 2 cycles). Triplicate ECGs will be performed at screening, baseline (prior to dose on Day 1) and right before serial PK draws on each day of dosing. All triplicate ECG tracings will be sent to an independent ECG core laboratory for blinded manual interval measurements. The active safety monitoring duration will be up to 36 days after the last dose of GO or starting of subsequent anticancer therapy, including consolidation and/or conditioning regimens. This study includes the collection of hemorrhage-related laboratory data and coagulation-related assessments, such as CBC and differential counts, PT, aPTT, and fibrinogen. Any event of VOD/SOS will continue to be reported as SAE during the entire study duration.

[figure not shown]
After receiving the study treatment (Cycle 1 and Cycle 2, if administered), blood cell and differential counts will be examined 3 times a week after GO dosing until having determination of remission status (see [Section 7.5](#)); subsequently CBC and differential counts will be collected once weekly until 36 days after the last dose of GO or until start of subsequent anticancer therapy, eg, consolidation or conditioning regimen. Efficacy evaluation and final determination of remission status by blood and bone marrow aspiration (and biopsy if applicable) will be conducted after recovery of blood counts is observed or at a maximum of 36 days after the last dose of GO treatment (EOT). Study duration for each patient is a total of 12 months from enrollment, survival data will be collected for the study duration of 12 months.

Treatment Plan

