Other severe or life-threatening non-hematologic toxicities	
 • Delay treatment with GO until recovery to a severity of no more than mild (Grade ≤ 1). • Omit scheduled dose if delayed more than 2 days between sequential infusions.
Hematologic Toxicities	Recommended Actions
Persistent thrombocytopenia	
 • If platelet count does not recover to greater than or equal to $50,000/\mu\text{L}$ within 42 days after the last dose of GO in the first cycle, DO NOT administer the 2nd cycle.*
Persistent neutropenia	
 • If neutrophil count does not recover to greater than or equal to $1,000/\mu\text{L}$ within 42 days after the last dose of GO in the first cycle, DO NOT administer the 2nd cycle.*

* except in patients with the bone marrow blasts $\geq 5\%$, the decrease in neutrophils and platelets thought to be due to the underlying leukemia.

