### **3.5.2.1. Time to Recovery of Neutrophils**

For patients who respond, time to recovery of neutrophils for each cycle will be defined as the date of first dose of study treatment to the date that the absolute neutrophils recover to counts of 500/ $\mu$ l after each cycle. During each cycle, the nadir will be calculated. Recovery is not considered to have occurred until after the date of this nadir. If the nadir equals or exceeds the target level of recovery, the date of recovery is defined as the first date after the final dose in the cycle on which the target level was reached. Patients not achieving the target levels of neutrophil recovery are censored at the last laboratory evaluation prior to the next cycle, first follow-up anti-cancer treatment, or death, whichever comes first.

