#### 6.6.3.1. Time To Recovery

The analysis of Time to Recovery of Neutrophils and the analysis of Time to Recovery of Platelets will be similar, therefore this section is written generically as “Time to Recovery”.

Time to Recovery for responders will be reported in days and derived as ((recovery date or censoring date) – date of first dose +1) for each cycle (for responders in that cycle).

The summary will include the number of patients recovered to the level of interest and the number of patients not recovered and reported for the safety analysis set.

Time to Recovery will be summarized using the Kaplan-Meier method. The quartiles will be estimated by the Kaplan-Meier method. Confidence intervals (95%) for quartiles will be based on the Brookmeyer-Crowley method.

The estimated survival curves will be displayed graphically (unless there are  $<$  5 responders) with one graph including estimates for the adult and pediatric patients separately. Graphs will describe the number of patients at risk over time.

**Prolonged Cytopenias (Neutrophils and Platelets):** For each cycle, patients with Time to Recovery longer than 42 days will be considered prolonged and summarized for the safety analysis set. The percentage will be based on a denominator that will exclude patients without data to determine the status at Day 42 relative to the cycle start. Thus prolonged cytopenias applies only to patient who are responders in the respective cycle.

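### The prolonged-cytopenia percentage can leave out only responders still unrecovered when counts stop, so under non-informative censoring it is biased low

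*SAP*

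**What the plan says.** SAP 6.6.3.1 defines prolonged cytopenia separately for neutrophils and platelets and for each cycle: "patients with Time to Recovery longer than 42 days will be considered prolonged and summarized for the safety analysis set". Time to recovery is "derived as ((recovery date or censoring date) – date of first dose +1) for each cycle", and the percentage uses "a denominator that will exclude patients without data to determine the status at Day 42 relative to the cycle start". The summary covers only responders in the cycle concerned.

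SAP 3.5.2.1 sets the neutrophil target at 500/µL and the censoring rule: "Patients not achieving the target levels of neutrophil recovery are censored at the last laboratory evaluation prior to the next cycle, first follow-up anti-cancer treatment". An earlier death also censors. SAP 3.5.2.2 does the same for platelets at 50,000/µL and also requires seven days without a platelet transfusion.

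Protocol Section 3 limits how long counts are scheduled. Once remission status is determined they are "collected once weekly until 36 days after the last dose of GO or until start of subsequent anticancer therapy". The Table 2 footnotes add that "EOT is defined as 36 days after the last dose of GO", and the visit window is ±2 days.

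For the same time-to-recovery variable, SAP 6.6.3.1 plans Kaplan-Meier quartiles and curves. It does not ask for the Kaplan-Meier estimate at Day 42, and it plans no bounds or sensitivity analysis for the percentage.

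**The concern.** Dropping patients with unknown status is harmless when the reason for not knowing is unrelated to the result. Here it is related. Early recovery settles a patient's status for good, whereas a patient who has not recovered must be followed to Day 42 to be counted. The threshold also lies next to the scheduled end of counts, so small shifts in the calendar decide who is counted.

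Safety is a secondary objective and myelosuppression is an adverse event of special interest (SAP 3.5.1.1). Protocol 1.2.2.4 cites faster count recovery with the fractionated regimen (medians of 23 and 20 days, against 40.5 and 51 days in the earlier studies). A prolonged-cytopenia percentage is likely to be quoted beside those medians, and an understated one would flatter the regimen.

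**Working it through.** The plan states no expected rate of prolonged cytopenia, so there is no figure of its own to reproduce.

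**1. When counts end.** EOT day = day of last dose + 36, ±2 (Protocol Tables 1 and 2).

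| Last dose in cycle | EOT | Window |
|---|---|---|
| Day 7 (on time) | Day 43 | 41–45 |
| Day 4 (Day 7 dose omitted, Protocol Table 3) | Day 40 | 38–42 |
| Day 1 only | Day 37 | 35–39 |

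With on-time dosing, only an EOT on Day 41 falls short. An unrecovered patient seen at EOT on Day 42 or later has a known status and is counted as prolonged. Next therapy or death can end counts earlier.

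**2. Who can be dropped.** Let T be the recovery day and C the day of the last count.
- T ≤ 42 and T ≤ C: kept, not prolonged.
- T > 42 and C ≥ 42: kept, prolonged.
- C < 42 and T > C: dropped.

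Everyone in the third group is unrecovered at the last count.

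**3. Direction.** Planned rate = P(T>42, C≥42) / [P(T>42, C≥42) + P(T≤42, T≤C)]. Let S = P(T>42), F = 1 − S and G = P(C≥42). If C is independent of T, the numerator is S·G. The last term is F·G + P(T≤C<42), which is at least F·G. So the planned rate is at most S·G/(S·G + F·G) = S. Equality needs P(T≤C<42) = 0, in practice that no counts end before Day 42.

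**4. Example in counts.** Assume the response rate in Protocol 1.2.2.4: 19/57 × 50 = 16.7, about 17 adult responders. Suppose 13 recovered by Day 42, 2 were seen unrecovered at Day 42 or later, and 2 were censored unrecovered earlier.
- Planned: 2/(13 + 2) = 13.3%.
- Best case: 2/17 = 11.8%.
- Worst case: 4/17 = 23.5%.

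If all four unrecovered patients were censored early, the planned figure would be 0/13 = 0%, with a worst case of 4/17 = 23.5%.

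**5. Illustrative size.** The inputs below are assumptions, apart from the 23-day median. Recovery is lognormal with that median, EOT is uniform over the ±2 days, and next therapy starts on Days 25–41 independently of recovery (1,000,000 simulated patients per setting).

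| Setting | True 5% | True 10% | True 20% |
|---|---|---|---|
| EOT window only | 4.0% | 8.2% | 16.7% |
| 10% omit Day 7 dose, 10% early therapy | 3.4% | 7.0% | 14.5% |
| 10% omit, 20% early therapy | 3.1% | 6.4% | 13.3% |
| 10% omit, 40% early therapy | 2.4% | 5.0% | 10.6% |

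The first row can be checked by hand. One EOT day in five falls before Day 42, so a true 10% becomes about 0.8 × 0.10/(0.8 × 0.10 + 0.90) = 8.2%. Kaplan-Meier at Day 42 returned the true rate in every setting, and no recovered patient was dropped.

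A second set of assumptions used log-SD 0.5, medians of 23 or 30 days, and 0%, 30% or 50% starting therapy over Days 25–60. It gave 9.2%, 8.1% and 7.4% for a true 11.3%, and 21.2%, 19.2% and 17.7% for a true 25.1%. The relative shortfall runs from (25.1 − 21.2)/25.1 = 16% to (11.3 − 7.4)/11.3 = 35%.

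**6. The other end of the range.** If everyone still unrecovered has a count on or after Day 42, nobody is dropped and the shortfall is zero.

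**The case against.** The strongest reply is that the protocol closes most of these routes.

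- **Next therapy.** Protocol 5.7 bars anticancer therapy until remission status is determined by marrow. Protocol 7.5 and SAP 3.2.3 time that marrow to neutrophils of at least 500/µL and platelets of at least 50,000/µL, the same levels as SAP recovery, or to 36 days after the last dose at the latest. Therapy in an unrecovered responder before Day 42 therefore needs an early marrow. Protocol Section 3 also recommends at least two months between the last dose and HSCT.
- **End of counts.** Protocol 6.2.4 requires safety laboratory data through at least 36 days after the last dose or to the start of next therapy, which is Day 43 for on-time dosing. Protocol 7.4 asks for abnormal values to be repeated until they resolve, return to baseline or reach Grade 1 or lower. The SAP censors at the last evaluation, not at EOT, so later counts are usable.
- **Cycle 2.** Entry requires counts at or above the recovery targets. The exception is for marrow blasts of at least 5%, which rules out response. Only transfusion-dependent platelets leave a gap.
- **Numbers.** CR requires counts above both targets, so mainly CRi patients are exposed. With 17 responders and a true rate of 11.3%, the gaps above amount to (11.3 − 9.2)% × 17 = 0.4 to (11.3 − 7.4)% × 17 = 0.7 of a patient. No decision rule uses the percentage.
- **Kaplan-Meier is already planned**, and Day 42 can be read off the curve.

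Most of this stands as a limit on size. It does not remove the fault. The protocol wording makes early therapy unlikely but does not forbid it. An EOT on Day 41, an omitted Day 7 dose, death and transfusion dependence remain. A reader will quote the printed percentage before reading a value off a curve, and the curve is not drawn when there are fewer than five responders.

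**Conclusion.** The denominator rule is outcome-dependent, and under non-informative censoring the percentage is biased low. That conclusion rests on the ordinary reading of the rule, in which a patient with recorded recovery by Day 42 has a determined status. The size cannot be fixed from the documents. It runs from zero to about half the true rate under the assumptions tried, and is probably towards the lower end if sites follow the marrow timing and repeat abnormal counts. This is a modest fault in a descriptive safety summary.

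A reader might infer three stronger things that the documents do not support.

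- **That the percentage can only err downward.** If the dropped patients were about to recover, it errs upward: 13.3% against 11.8% in the example above.
- **That an understatement of about 15% to 35% is to be expected.** That range comes from letting therapy start independently of recovery and letting counts stop at Day 41 in a fifth of patients.
- **That the SAP contradicts Protocol Table 3,** which counts "within 42 days after the last dose of GO in the first cycle", about Day 7 + 42 = Day 49. That rule governs whether Cycle 2 may be given. The SAP endpoint states its own clock, from the start of the cycle.

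Nor does the point undermine the comparison of median recovery times. The planned Kaplan-Meier quartiles already allow for censoring there.

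**What to change.** In SAP 6.6.3.1, for each cycle and cell line:

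1. Report the Kaplan-Meier probability of non-recovery at Day 42 of the cycle among responders, with a 95% log(-log) confidence interval (the method in SAP 5.2.13). Use it in place of the current percentage, or as the primary figure above it.
2. Give the number of responders censored unrecovered before Day 42.
3. Give best-case and worst-case counts over all responders in the cycle, treating those patients first as recovered by Day 42 and then as prolonged.
4. Where responders are too few, for example fewer than five as already used for the curves, give the counts and bounds only.

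The cost is SAP wording and a few rows from data and methods already planned, with no new blood draws. The reported rate may be somewhat higher. The Day 42 estimate will be unstable in small groups such as Cycle 2 or the pediatric patients, and it is undefined if the longest follow-up is censored before Day 42. Kaplan-Meier also treats death and next therapy as non-informative censoring, which is why the bounds should accompany it.

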#### 6.6.3.2. Hy's Law Assessment

**Liver function tests:** Alanine aminotransferase (ALT), aspartate aminotransferase (AST), Alkaline Phosphatase (ALP), and total bilirubin (TBILI) are used to assess possible drug induced liver toxicity.

An evaluation of drug-induced serious hepatotoxicity (eDISH) by scatterplots of using all data from the on treatment period will be produced to assess hepatotoxicity and to identify any potential Hy's Law cases. This summary does NOT indicate actual Hy's law cases.

- Maximum serum ALT vs maximum total bilirubin including reference lines at ALT=3×ULN and total bilirubin=2×ULN.
- Maximum serum AST) vs maximum total bilirubin including reference lines at AST=3×ULN and total bilirubin=2×ULN.

In addition, a listing of all total bilirubin, ALT, AST and alkaline phosphatase values for patients with a post-baseline total bilirubin  $\geq 2\times$ ULN, ALT  $\geq 3\times$ ULN or AST  $\geq 3\times$ ULN will be provided.

Summary of liver function tests will include the following categories. The number and percentage of patients with each of the following during the on-treatment period will be summarized:

- ALT  $\geq 3\times$ ULN, ALT  $\geq 5\times$ ULN, ALT  $\geq 10\times$ ULN, ALT  $\geq 20\times$ ULN
- AST  $\geq 3\times$ ULN, AST  $\geq 5\times$ ULN, AST  $\geq 10\times$ ULN, AST  $\geq 20\times$ ULN
- (ALT or AST)  $\geq 3\times$ ULN, (ALT or AST)  $\geq 5\times$ ULN, (ALT or AST)  $\geq 10\times$ ULN, (ALT or AST)  $\geq 20\times$ ULN
- TBILI  $\geq 2\times$ ULN
- Concurrent ALT  $\geq 3\times$ ULN and TBILI  $\geq 2\times$ ULN
- Concurrent AST  $\geq 3\times$ ULN and TBILI  $\geq 2\times$ ULN
- Concurrent (ALT or AST)  $\geq 3\times$ ULN and TBILI  $\geq 2\times$ ULN
- Concurrent (ALT or AST)  $\geq 3\times$ ULN and TBILI  $\geq 2\times$ ULN and ALP  $> 2\times$ ULN
- Concurrent (ALT or AST)  $\geq 3\times$ ULN and TBILI  $\geq 2\times$ ULN and ALP  $\leq 2\times$ ULN or missing

Concurrent measurements are those occurring on the same date.

Categories will be cumulative, i.e., a participant with an elevation of AST  $\geq 10\times$ ULN will also appear in the categories  $\geq 5\times$ ULN and  $\geq 3\times$ ULN. Liver function elevation and possible Hy's Law cases will be summarized using frequency counts and percentages.

Summary of liver function tests will also be provided by Cycle (1, 2, Follow-up).

#### 6.6.4. Vital Signs

Vital sign data will be listed as needed to be compliant with ICH required listings and not summarized.

### **6.6.5. Electrocardiogram**

This section describes all ECG parameter summaries including secondary analyses of changed from baseline in QTc. Refer to Section 6.1.1 for the primary endpoint analysis. As noted in Section 5.2, separate summaries for adult and pediatric patients will be presented. As noted in Section 5.2.8.1, a study specific QT interval correction will be evaluated only for adult patients. All analyses will be provided for the QTc analysis set. All summaries will be based on the ECG core laboratory (vendor) results for ECG parameters.

#### **6.6.5.1. Assessment of Correction Factors**

Scatterplots of QTc (QTcB, QTcF, QTcS) versus RR interval (msec) using individual replicates (non-averaged) from the timepoint selected as baseline including the linear regression line with description including slope and its 95% CI, intercept, and coefficient of determination ( $R^2$ ) will be presented.

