9.3.1. Analysis of Primary Endpoint

ECG measurements from the ECG core laboratory (an average of the triplicate measurements) will be used for the statistical analysis and all data presentations. Only the scheduled ECGs will be used in the primary analysis. The last available planned triplicate measurements prior to first dose will be used as baseline.

QT measurements will be corrected by heart rate (QTc) including Bazzett's (QTcB) and Fridericia's (QTcF) methods, and a study-specific correction method (QTcS) will be evaluated according to the observed data. QTcF will be used for the primary analysis.

The absolute corrected QT interval and changes in QTc (QTcB, QTcF, and/or QTcS) from baseline will be summarized using descriptive statistics by nominal time point.

A random effect model with the nominal timepoints as a fixed effect and patients as a random effect will be used for the primary analysis to estimate the mean change in QTcF (primary endpoint) at the post baseline nominal timepoints (Day 4, 0 hours, and Day 7, at 0, 2, 4 and 6 hours) along with 2-sided 90% confidence interval for the mean. The maximum increase in QTc from baseline will be computed over all time points. The maximum increase from baseline will be summarized with descriptive statistics.

Categorical analysis of changes in QTc (QTcB, QTcF, and/or QTcS) from baseline including absolute QTc interval prolongation and maximum increase will be provided. Interval measurements from unscheduled ECGs will be included in the categorical analyses.

Baseline versus worst on treatment QTc according to maximum CTCAE grade will be summarized using a shift table.

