### 5.1. Hypotheses and Decision Rules

The primary QTc analysis will be based on a non-inferiority hypothesis testing framework. If the upper bounds of one-sided 95% confidence intervals of change from baseline in QT measurements using Fridericia's heart rate correction for adult patients for each of the QTc

sampling time points (Day 4, 0 hours, and Day 7, at 0, 2, 4 and 6 hours) from Cycle 1 are below 20 msec, the post dose QTc interval will be considered to be “non-inferior” to the baseline; the QTc effect of GO will be concluded to be not unacceptable.

Thus with an overall 1-sided significance level of 0.05 and a non-inferiority margin of 20 msec, assuming a standard deviation of 18.8 msec and a mean change from baseline for QTcF up to 10 msec, 50 adult patients will provide 90 % power for assessing the 5 QTc sampling timepoints using paired difference in means with the t distribution. **CCI**

The inclusion of 6 additional pediatric patients ( $12 \leq \text{age} \leq 17$  years) was determined based on agreement with CHMP.

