### **5.2.8. ECG Derivation Details**

#### **5.2.8.1. Corrected QT interval derivation**

$$\text{Fridericia's heart rate correction: } \frac{QT}{\sqrt[3]{60/HeartRate}}$$

$$\text{Bazzett's heart rate correction: } \frac{QT}{\sqrt{60/HeartRate}}$$

The ECG core laboratory (vendor) will provide the corrected QT intervals according to the Fridericia’s and Bazzett’s corrections.

A study specific correction for adult patients will be derived as  $QT/(RR)^S$  where S is determined as follows:

The study specific QT correction factor (ICH E14 Step 4, May 12, 2005) will be derived for adult patients in the QTc analysis set using the individual replicates from the selected baseline (baseline is defined in Section 3.4) QT and RR.

No study specific QT correction factor will be assessed for the 6 pediatric patients.

Prior to estimating the regression, QT and RR will be transformed by the natural logarithm to  $\ln(QT)$  and  $\ln(RR)$ , respectively.  $\ln(RR)$  will be treated in the regression as the explanatory variable with  $\ln(QT)$  as the response variable. The regression equation will be as follows:

$$\ln(QT) = \text{Intercept} + S \times \ln(RR) + \text{Error}$$

Where S = slope of the regression line.

Once (S) is estimated, it will be used to derive the study specific QT correction, QTcS, for adult patients in the QTc analysis set.

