#### **5.2.8.2. Averaging of triplicate ECG parameter measurements**

After the above variables have been derived within each patient and scheduled timepoint, each ECG parameter (including QTcF, QTcB, QTcS, QT, HR, PR, RR, QRS) should each be averaged as follows:  $(1^{\text{st}} \text{ measurement} + 2^{\text{nd}} \text{ measurement} + 3^{\text{rd}} \text{ measurement}) / 3$ . All summary statistics, analyses and figures will be based on the triplicate averaged data from the ECG core laboratory.

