## 6.1. Primary Endpoint

### 6.1.1. Change in QTcF from baseline

ECG measurements from the ECG core laboratory (an average of the triplicate measurements) will be used for the statistical analysis and all data presentations. Only the scheduled ECGs from adult patients in Cycle 1 and the particular timepoints of Day 4, 0 hours, and Day 7 at 0, 2, 4, and 6 hours will be interpreted for the primary analysis. The last available planned triplicate measurements prior to first dose will be used as baseline.

QT measurements will be corrected by heart rate (QTc) according to Fridericia's (QTcF) method.

A linear model (for adult patients and pediatric patients separately) with the Cycle 1 nominal timepoints as a fixed effect and unstructured variance/covariance to account for the repeated measurements from patients will be used for the primary analysis to estimate the mean change in QTcF (primary endpoint) at the post baseline nominal timepoints for Cycle 1 along with the estimated least squares means and 2-sided 90% confidence interval for the mean. Confidence intervals will use the approximate t distribution with degrees of freedom by Kenward Rogers method. Refer to Section 5.2.8 for further details of derivations. Although the 90% CI for the mean change in QTcF from the Cycle 1 Day 4, 0 hours, and Cycle 1 Day 7, at 0, 2, 4 and 6 hours summarized for adult patients will be interpreted (see Section 5.1), all Cycle 1 timepoints will be included in the estimation.

Summary will be for the QTc analysis set. The least squares mean and its 90 % confidence interval will be displayed graphically.

Additional summaries of QT interval data are described in Section 6.6.5 along with the summary of other ECG data.

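### The 95% CI for the QTc–RR slope in SAP 6.6.5.1 makes no allowance for three replicates per patient; as written it is too narrow for QTcF and QTcB, with descriptive consequences only

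*SAP*

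**What the plan says.** SAP 6.6.5.1 (Assessment of Correction Factors) plots QTcB, QTcF and QTcS against RR "using individual replicates (non-averaged) from the timepoint selected as baseline including the linear regression line with description including slope and its 95% CI", together with the intercept and R². It names no method for the interval.

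The replicates come from the triplicate ECG. The footnotes to Protocol Table 2 specify that "three consecutive 12-lead ECGs will be performed approximately 2 minutes apart, but within 15 minutes for all ECGs".

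The companion regression in SAP 5.2.8.1, which estimates the exponent for QTcS in adults, is also fitted "using the individual replicates from the selected baseline". It takes "S = slope of the regression line" from a model with one error term and no patient term. It uses S as a point estimate and plans no interval for it.

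Two other places in the SAP contrast with this:

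- The primary model in 6.1.1 specifies "unstructured variance/covariance to account for the repeated measurements from patients", and 6.6.5.3 does the same for the QTcB and QTcS change-from-baseline models.
- Section 5.2.8.2 states a general rule: "All summary statistics, analyses and figures will be based on the triplicate averaged data from the ECG core laboratory". Section 6.6.5.1 departs from it without saying so.

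On the role of the corrections, Protocol 9.3.1 says "QTcF will be used for the primary analysis".

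**The concern.** The display exists to show whether each correction removes the dependence of QTc on heart rate, and the slope interval is the only measure of uncertainty it offers. Three ECGs from one patient within 15 minutes share that patient's RR level and QTc level. Ordinary regression counts them as three independent observations, so it reports more precision than about 50 patients can give.

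At stake is the error rate of an informal reading. If QTcF is truly flat against RR, a correct 95% interval excludes zero 5% of the time. An interval with 84% coverage does so 16% of the time, and one with 75% coverage 25% of the time. The report could then show residual rate dependence in QTcF, or in QTcB, that arose by chance. In a study whose purpose is a QT assessment, that would invite avoidable questions.

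**Working it through.** **The plan's own figure.** The SAP gives no width or coverage for the slope interval beyond the nominal 95%. The related design figure is that "50 adult patients will provide 90 % power for assessing the 5 QTc sampling timepoints using paired difference in means with the t distribution". With a margin of 20 msec, an assumed mean change of 10 msec, SD 18.8 msec and one-sided 5%:

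- Noncentrality = (20 − 10)/(18.8/√50) = 10/2.659 = 3.76.
- Power at one time point, t with 49 df = 0.9805.
- Five time points treated as independent: 0.9805⁵ = 0.906, against the stated 90%.

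This reproduces. Its unit is the patient (n = 50), and the slope does not enter it.

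**Inputs for the slope interval**

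- Patients: about 50 adults (SAP 5.1).
- Replicates per patient: m = 3 (Protocol Table 2), so 50 × 3 = 150 points.
- Within-patient correlation (ICC) of RR and of the regression residuals: not in the documents. Assumed, with a range shown.

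**Formula.** For ordinary least squares on clusters of size m, the large-sample variance of the slope is understated by the design effect

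DEFF = 1 + (m − 1) × ICC_RR × ICC_resid = 1 + 2 × ICC_RR × ICC_resid.

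The standard error is understated by √DEFF, and actual coverage is about 2Φ(1.96/√DEFF) − 1. Example with both ICCs at 0.7: DEFF = 1 + 2 × 0.49 = 1.98, √1.98 = 1.407, coverage = 2Φ(1.393) − 1 = 83.6%.

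**Simulation.** 50 patients × 3 replicates, normal errors, one common slope, 10,000 runs per setting. The clustered interval uses t with 49 df.

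| Both ICCs (assumed) | √DEFF | Coverage, formula | Coverage, simulated | Coverage, clustered SE | Clustered width ÷ ordinary width |
|---|---|---|---|---|---|
| 0.3 | 1.09 | 92.9% | 93.0% | 94.3% | 1.08 |
| 0.5 | 1.22 | 89.0% | 88.6% | 93.5% | 1.21 |
| 0.7 | 1.41 | 83.6% | 83.5% | 94.3% | 1.39 |
| 0.8 | 1.51 | 80.6% | 81.1% | 93.8% | 1.49 |
| 0.9 | 1.62 | 77.4% | 76.0% | 93.3% | 1.60 |
| 0.95 | 1.67 | 75.8% | 75.2% | 93.1% | 1.66 |
| 1 (limit) | 1.73 | 74.2% | – | – | – |

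Three further results:

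- With no within-patient correlation in RR (ICC_RR = 0, ICC_resid = 0.8), the ordinary interval covers 95.1%. Both correlations must be positive for the problem to arise.
- The bound √3 = 1.73 is the large-sample value. With exactly 50 patients and identical replicates, the degrees of freedom move it slightly, to √(148/48) = 1.76.
- Regression on the triplicate averages covers about 95%. Its interval is about 1.79 times the ordinary one in every equal-ICC setting, so at low correlation it is much wider than the clustered interval (1.79 against 1.08 at 0.3).

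**QTcS.** Since QTcS = QT/RR^S, ln QTcS = ln QT − S × ln RR. On the replicates used to fit S, the slope of ln QTcS on ln RR is S − S = 0. On the plotted msec scale it is close to zero. In 2,000 simulated data sets of 50 × 3 the ordinary interval never excluded zero (largest |t| 0.75).

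**The case against.** **Independence is inferred.** Section 6.6.5.1 does not say how the interval is computed. This is true. But an unqualified linear regression line is most naturally read as ordinary least squares, 5.2.8.1 writes a single error term for the companion fit, and the SAP names an adjustment for repeated measurements where it intends one. A programmer following the text would produce the unadjusted interval.

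**No decision depends on it.** This stands in full. The interval has no threshold, test or selection rule attached. A reader might infer that a misleading slope could displace QTcF or weaken the primary conclusion. The documents do not support that: QTcF is fixed in advance, and the 20 msec rule in SAP 5.1 uses QTcF alone. The wording QTcB and/or QTcS in 6.6.5.3 leaves open which secondary corrections are shown, but it is not tied to this interval.

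**The size is unknown.** This also stands. A reader might call the interval far too narrow. Assuming RR SDs of 120 between and 20 to 40 within patients, and QTcF SDs of 15 to 18 between and 4 to 8 within, gives coverage of 75 to 79%. Those values imply ICCs of 0.90 to 0.97 (14400/16000 to 14400/14800) and 0.78 to 0.95 (225/289 to 324/340). None of these SDs is in the documents. High correlation is plausible for ECGs about two minutes apart, but it remains an assumption.

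**Individual replicates were chosen on purpose.** SAP Table 1 records this for the derivation of S. That supports keeping them in the plot and in the fitted slope. It does not justify an interval that ignores which patient they came from.

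**Conclusion.** Wrong as written, minor. Followed literally, 6.6.5.1 labels as 95% an interval that covers less than that whenever RR and the QTc residuals are both positively correlated within patients. Under assumed equal ICCs of 0.3, 0.5, 0.7 and 0.9 to 0.95, coverage is about 93%, 89%, 84% and 75%. The result rests on reading the fit as ordinary regression, on about 50 adults with complete triplicates, and on ICCs that the documents do not give.

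The effect is confined to the descriptive assessment of QTcF and QTcB. It does not extend to the QTcS slope, to the point estimate of any slope, to the primary QTcF analysis or to the 20 msec test. A reader might also take S in 5.2.8.1 to be affected. It is not: ignoring the clustering does not bias S, and no interval for it is planned.

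**What to change.** In SAP 6.6.5.1, keep the replicate scatterplot and the fitted slope. Add that the 95% CI for the slope is computed with patient-clustered standard errors or a patient-level bootstrap, and that this display is an exception to the averaging rule in 5.2.8.2.

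Fitting the triplicate averages would also restore coverage. It costs more width at low correlation, and it would assess QTcS on data other than the replicates used to fit S, so the clustered interval suits the planned display better.

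The cost is one sentence of SAP text, one programming option and a wider interval: 1.08 to 1.66 times the ordinary width over the assumed range. In the simulation the clustered interval covered 93 to 94%, slightly below nominal; the bootstrap was not simulated. No extra data are needed, and the sample size and primary analysis do not change.
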